10.2 SERIOUS ADVERSE EVENTS

10.2.1 Definition

A serious adverse event (SAE) is any adverse event (experience) that in the opinion of either the investigator or sponsor results in **ANY** of the following:

- Death
- A life-threatening adverse event (experience). Any AE that places a participant or participants, in the view of the Investigator or sponsor, at immediate risk of death from the reaction as it occurred. It does **NOT** include an AE that, had it occurred in a more severe form, might have caused death.
- Inpatient hospitalization or prolongation of existing hospitalization (for > 24 hours)
- A persistent or significant incapacity or substantial disruption of the ability to conduct normal life functions
- A congenital anomaly or birth defect
- Important Medical Event (IME) that, based upon medical judgment, may jeopardize the participant and may require medical or surgical intervention to prevent one of the outcomes listed above

10.2.2 Reporting Serious Adverse Events

All new SAEs occurring from the date of the HPPH study drug infusion until 30 days after the HPPH Drug infusion, or PDT light treatment, will be reported to the IRB, in accordance to RPCI guidelines. The RPCI SAE Source Form is to be completed with all available information, including a brief narrative describing the SAE and any other relevant information.

SAEs occurring after the 30 day follow up period that the investigator determines to be possibly, probably or definitely related to the study intervention should be reported.

SAE's identified as an Unanticipated Problem by the Investigator must be reported. Please refer to **Section 10.5** for details on reporting Unanticipated Problems.

10.4 FOLLOW-UP FOR SERIOUS ADVERSE EVENTS

All related SAEs should be followed to their resolution, until the study participant is lost to follow-up, the start of a new treatment, or until the study investigator assesses the event(s) as stable or irreversible. New information will be reported when it is received.

10.5 UNANTICIPATED PROBLEMS

10.5.1 Definition

An Unanticipated Problem (UP) is any incident, experience, or outcome that meets all of the following criteria:

- Unexpected (in terms of nature, severity, or frequency) given:

- a) The research procedures that are described in the study-related documents, including study deviations, as well as issues related to compromise of participant privacy or confidentiality of data.
- b) The characteristics of the population being studied.
- Related or possibly related to participation in the research (possibly related means there is a reasonable possibility that the incident, experience, or outcome may have been caused by the procedures involved in the research).
- Suggests that the research places participants or others at a greater risk of harm (including physical, psychological, economic, or social harm) than was previously known or recognized and if in relation to an AE is also deemed **Serious** per **Section 10.2**.

10.5.2 Reporting Unanticipated Problems

Unanticipated problem reporting will begin at the time of participant consent. The Reportable New Information (RNI) Form will be submitted to CRS Compliance Office within 1 business day of becoming aware of the Unanticipated Problem. After review, CRS Compliance will submit the RNI to the IRB.

When becoming aware of new information about the Unanticipated Problem, submit this updated information to CRS Compliance with an updated Reportable New Information Form. The site Investigator or designated research personnel will report all unanticipated problems, whether related or unrelated to the investigational agent(s) to the **IRB in accordance with their local institutional guidelines**.

10.6 SAFETY STOPPING RULE

If 20% of patients randomized to the PDT arm fail treatment and require salvage surgery at any one institution with 50% of their accrual target, the RPCI DSMB will suspend the study for further evaluation.

10.7 FDA REPORTING

This protocol is being conducted under a RPCI IND, and RPCI will be responsible for reporting certain AEs or Unanticipated Problems to the FDA. RPCI's Compliance Office will report Network Site reports to the FDA.

The following describes the FDA reporting requirements by timeline for AEs and new safety findings that meet the criteria outlined below:

Within 7 Calendar Days

Any adverse event that meets **ALL** the following criteria:

- Related or possibly related to the use of the study drug;
- Unexpected; and
- Fatal or life-threatening.

Within 15 Calendar Days

Any adverse event that meets **ALL** the following criteria:

- Related or possibly related to the use of the study drug;
- Unexpected; and
- Serious but not fatal or life-threatening.

Or meets **ANY** of the following criteria:

- A previous adverse event that is not initially deemed reportable but is later found to fit the criteria for reporting (report within 15 days from when event was deemed reportable).
- Any findings from other studies, including epidemiological studies, pooled analysis of multiple studies, or other clinical studies conducted with the study drug that suggest a significant risk in humans exposed to the drug.
- Any findings from animal or in vitro testing that suggest a significant risk for human participants including reports of mutagenicity, teratogenicity, or carcinogenicity or reports of significant organ toxicity at or near the expected human exposure.
- Any clinically important increase in the rate of occurrence of a serious, related or possibly related adverse event over that listed in the protocol or investigator brochure.

Sponsors are also required to identify in IND safety reports, all previous reports concerning similar adverse events and to analyze the significance of the current event in the light of the previous reports.

Reporting Process

The principal investigator or designee will complete and submit a FDA Form 3500A MedWatch for any event that meets the above criteria. Forms will be submitted to the CRS Compliance Office via email: [contact].

11 DATA AND SAFETY MONITORING BOARD

The RPCI Data and Safety Monitoring Board will assess the progress of the study, the safety data, and critical efficacy endpoints. The DSMB will review the study annually and will make recommendations that include but not limited to; (a) continuation of the study, (b) modifications to the design (c) or termination of the study.

12 STATISTICAL METHODOLOGY

The primary objective of this study is test the non-inferiority of PDT to standard of care by comparing the rate of tumor response after PDT to those obtained after surgery, at 24 months post treatment. The secondary objectives are to compare QoL after PDT or surgery at 6, 12, 18, and 24 months post-procedure, and to assess the toxicity using the CTEP NCI Common Terminology Criteria for Adverse Events (CTCAE Version 4.0).

12.1 JUSTIFICATION FOR THE STATISTICAL DESIGN AND THE NON-INFERIORITY MARGIN

In our previously published study we observed an 82% CR in patients with T1/T2 N0 SCC of the oral cavity treated with PDT and HPPH.¹⁸ We also reported a similar response rate when we used HPP-PDT to treat early stage laryngeal cancer.⁵² These response rates are in agreement with other studies using PDT in this indication (see **Table 1** in section **1.3**). All patients that failed to respond were successfully salvaged by surgery. Since the local recurrence rate after initial surgery is as high as 20%,⁷⁻⁹ we believe that it is reasonable to assume that 85% CR will be observed in both arms. We also wish to provide a bit of a cushion in case the surgical response rate is much higher than 85% given we are in an experimental setting.

In addition, we propose using the logic and rationale the FDA guidance documents propose for traditional phase III bioequivalence trials in terms of our trial design. The FDA refers to various rules such as the 80/20 rule, 75/75 rule, where the generic drug needs to be within 20% of the brand product relative to specified pharmaceutical measures. For a phase III trial the standard 80/20 rule translates to approximately a 17 percentage point difference. The 75/75 rule yields roughly a 21 percentage point difference. Hence, in the phase II setting we believe a 20-point difference is reasonable in terms of determining whether or not a confirmatory large-scale phase III trial with a tighter equivalence window should be put forward as a next step. The information gained from this study will be used for a larger scale phase III equivalence trial in terms of planning and sample size calculations with a tighter equivalence threshold. In terms of safety, it should be noted that patients that fail PDT can be effectively salvaged with surgery, in a timely manner.

12.2 SAMPLE SIZE DETERMINATION

In the proposed randomized trial, participants will be randomized to the treatment arms using a stratified block randomization scheme, with blocking stratified by clinical site (RPCI, and two other participating sites). Participants will be included in data analyses according to their randomized treatment assignment irrespective of the treatment actually received (intent-to-treat). Exceptions would include those who withdraw their consent to use any of their data prior to receiving any study medication. Initiation of study treatment will take place as soon as possible following randomization. No method of imputation will be used for missing data. All available data from participants who fail to complete this study will be included in all safety summaries.

The safety of the interventions will be assessed through the evaluation of Grade 3 or higher toxicities deemed possibly related to treatment. Both efficacy (e.g., tumor response) and toxicity rates will be estimated using simple relative frequencies. The corresponding 95% confidence intervals for the estimated probabilities will be computed using the method proposed in Clopper and Pearson (1934).

The design for this study is based on a test for non-inferiority of PDT compared to standard of care with regards to tumor response at 24 months post-procedure. Justification for use of a non-inferiority trial is that PDT may be viewed as a potential replacement for standard of care if it is established as less toxic than the standard of care yet still providing acceptable efficacy. Let π_{SOC}

and π_{PDT} are the probabilities of tumor response in the standard of care and PDT groups, respectively. The hypotheses corresponding to the proposed non-inferiority trial are

$$H_0 : \pi_{PDT} \leq \pi_{SOC} - \Delta,$$
$$H_a : \pi_{PDT} > \pi_{SOC} - \Delta,$$

where Δ is the non-inferiority margin. Specifically, we will be using the approach of Farrington-Manning to test our hypothesis via a score based test.⁵³

Under the null hypothesis ($\pi_{PDT} = \pi_{SOC} - \Delta = \pi$) is the probability of observing a particular set of results. A non-inferiority margin of 20 percentage points will be utilized and the Farrington-Manning based test will be performed in conjunction with a 0.05 nominal significance level. In the event that the non-inferiority test is statistically significant, a test for superiority will be conducted. The samples sizes of the trial are set at 57 in the standard of care and PDT groups. With the proposed sample sizes, there is approximately 80% power associated with the non-inferiority test when the true tumor response probabilities are equal to 85% in both groups. The calculation was carried forth using SAS PROC POWER.

In the analysis of QoL simple data analyses will initially take place including individual participant-level profile plots and overall mean plots used to examining the mean structure. Formal statistical examination of longitudinal patterns will be done through the use of a mixed model. Restricted maximum likelihood estimation will be utilized in the model fitting procedures as implemented by SAS PROC MIXED (version 9.3). Once the model is fit, specific linear contrasts based on the estimated model parameters will be constructed and used to test hypotheses concerning between time points and between group comparisons. We acknowledge the possibility of informative missingness, that is, the probability of a particular observation being missing may be related to the health of the participant, and therefore analyses will be interpreted with caution. All tests will be two-sided and tested at a 0.05 nominal significance level. Standard diagnostic plots will be used to assess model fit and transformations of variables may be considered in order to meet statistical assumptions.

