4.1 STUDY DESIGN

This is an open-label, randomized, multicenter Phase II study of HPPH-mediated PDT in participants with lesions that are diagnosed as previously untreated T1 N0 or T2 N0 SCC of the oral cavity. Participants will be randomized at a ratio of 1:1, to be treated with either surgery (57 participants) or PDT with HPPH (57 participants). The randomization will be done at RPCI by the biostatistician. The study schema is depicted in **Figure 1**.

Participants will be treated on an outpatient basis. Rarely, those undergoing HPPH with PDT may require hospitalization but this will be decided on a case by case basis. Participants undergoing surgery may be hospitalized.

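### Intent-to-treat is the only efficacy set for the open-label non-inferiority test, so participants randomized to PDT who have surgery from the start would dilute the difference unseen; a pre-specified per-protocol analysis should accompany it.

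*Combined protocol and SAP*

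**What the plan says.** - **Analysis set.** Section 12.2: "Participants will be included in data analyses according to their randomized treatment assignment irrespective of the treatment actually received (intent-to-treat". The one exception is for participants who withdraw consent to use of their data before any study medication. Section 12.3 makes everyone randomized evaluable for response. No per-protocol set, as-treated set or sensitivity analysis for non-adherence appears in section 12 or elsewhere.
- **Design.** Section 4.1: "This is an open-label, randomized, multicenter Phase II study of HPPH-mediated PDT". The comparator is surgery.
- **Primary test.** Section 12.2 sets an absolute margin of 20 points. On the level it says that "the Farrington-Manning based test will be performed in conjunction with a 0.05 nominal significance level". Whether the test is one- or two-sided is not stated there. Later in the same section, in the quality-of-life paragraph, stands "All tests will be two-sided and tested at a 0.05 nominal significance level".
- **Size and power.** Section 12.2: "The samples sizes of the trial are set at 57 in the standard of care and PDT groups", and "there is approximately 80% power associated with the non-inferiority test when the true tumor response probabilities are equal to 85% in both groups".
- **Salvage.** Section 4.3 treats progression, local recurrence, partial response or no response after PDT as treatment failure. Section 12 does not repeat that rule for the 24-month endpoint.
- **Removal after randomization.** Section 4.3 drops and replaces participants with certain pathology findings or a need for additional therapy. Section 7.4 lists the same grounds for withdrawal, along with noncompliance and voluntary withdrawal.
- **Gap.** No section says how to score a participant who never receives the assigned treatment and takes the other one.

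**The concern.** In a superiority trial, analysing as randomized is usually conservative, because non-adherence pulls the arms together and makes a difference harder to show. In a non-inferiority trial the same pull works towards the claim. Participants and surgeons here know the assignment, and the two treatments are very different procedures. A participant assigned to PDT may therefore have surgery instead.

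Section 12.2 justifies the design by PDT's potential to replace standard of care with acceptable efficacy. That is largely a question about the treatment delivered. If initial crossovers are scored with their surgical outcome, part of the PDT arm's response rate comes from surgery, and the plan has no second analysis that would show it.

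**Working it through.** **Inputs.** From section 12.2: n = 57 per arm, margin 0.20, 85% response in both arms for power, nominal level 0.05. Assumed, because the documents give no figure: initial crossover c of 5, 10 or 15% of the PDT arm, with crossovers taking the surgical response rate.

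**1. The plan's own power, and the level it implies.** The Farrington-Manning power is Φ[(Δ − z·se0)/se1]. Here se0 uses the response rates fitted under the null (PDT = surgery − 0.20) and se1 uses the true rates.

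- With 85% in both arms, maximum likelihood under that constraint gives 0.708 for PDT and 0.908 for surgery.
- se0 = √[(0.708×0.292 + 0.908×0.092)/57] = 0.0714
- se1 = √[2×0.85×0.15/57] = 0.0669
- One-sided 0.025: (0.20 − 1.960×0.0714)/0.0669 = 0.90, power 81.5% (83.2% by exact enumeration).
- One-sided 0.05: (0.20 − 1.645×0.0714)/0.0669 = 1.23, power 89.1%.

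The stated power of about 80% is approximately reproduced at one-sided 0.025 and not at one-sided 0.05. The 0.025 figures are therefore the main ones below.

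**2. False-claim rate with initial PDT-to-surgery crossover.** Put the truth for treatment received at the margin: surgery 0.85, PDT 0.65. The PDT arm as randomized then has response rate

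p = (1 − c)×0.65 + c×0.85 = 0.65 + 0.20c.

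The rejection probability is the sum of the two binomial probabilities over all 58 × 58 outcomes in which the Farrington-Manning statistic exceeds its critical value.

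| Crossover c | PDT arm rate p | False claim, one-sided 0.025 | False claim, one-sided 0.05 |
|---|---|---|---|
| 0% | 0.65 | 2.6% | 5.2% |
| 5% | 0.66 | 3.4% | 6.7% |
| 10% | 0.67 | 4.5% | 8.5% |
| 15% | 0.68 | 5.8% | 10.7% |

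**3. Dependence on the scoring rule.** If crossovers were scored as non-responders, p = 0.65(1 − c), which is 0.6175 at 5% and 0.585 at 10%. At one-sided 0.025 the false-claim rate then falls to 0.9% and 0.3%. The direction of the effect turns on a rule that the plan does not state.

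**4. Salvage after failed PDT.** Under section 4.3 these participants remain failures, so they add nothing to p. To see why the rule should also stand in section 12, suppose that, contrary to 4.3, a share of the 35% who fail PDT were counted as responders at 24 months. At a quarter, p = 0.65 + 0.35×0.25 = 0.7375 and the false-claim rate at one-sided 0.025 is 21%. At a half, p = 0.825 and it is 70%.

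**5. The per-protocol companion.** If 5, 10 or 15% of each arm is excluded (54, 51 or 48 left), the same power formula at 85% in both arms gives 79.3, 76.9 or 74.3% at one-sided 0.025. The exact false-claim rate returns to between 2.4 and 2.6%, provided that crossover is unrelated to prognosis.

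**The case against.** The strongest reply is that intent-to-treat answers a legitimate question. For the effect of being assigned to PDT, the test keeps its level whatever participants later receive. That stands: the inflation exists only relative to the effect of treatment received.

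Three further points limit the concern.

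- **Any switching.** A reader might infer that every move from PDT to surgery biases the test. The documents do not support this. The move that the protocol plans for is salvage after failed PDT, and section 4.3 classes it as failure.
- **Two-way crossover.** A reader might also count participants moving from surgery to PDT. With 10% crossing each way (0.67 against 0.83), the false-claim rate would be 7.4% at one-sided 0.025 and 13.0% at 0.05. But section 7.1 gives HPPH to participants randomized to PDT, and section 6.4 forbids use other than as the protocol directs. These figures should not be relied on.
- **Unknown frequency and scoring.** Crossover may be rare, since section 12.2 asks for treatment to start soon after randomization. A participant who refuses PDT may also be withdrawn under section 7.4 and have no 24-month result, since nothing is imputed. The dilution is therefore a possibility that the plan leaves open, not an established outcome.

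None of this supplies the missing per-protocol analysis or the missing scoring rule.

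**Conclusion.** The point holds for initial PDT-to-surgery crossover. Intent-to-treat is the only efficacy set named, and nothing in the plan would reveal dilution from such participants. At one-sided 0.025 the size is modest at 5% crossover (2.6% to 3.4%) and somewhat more than double the nominal level at 15% (5.8%). These figures assume the crossover rates, a truth exactly at the margin, and crossovers responding like the surgical arm.

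A reader might conclude that the nominal level of the primary test is broken. It is not, for the effect of assignment. Nor is the analysed set cleanly intent-to-treat: the drop-and-replace rule in section 4.3 and the withdrawal rule in section 7.4 conflict with sections 12.2 and 12.3. Those rules are not a substitute for a per-protocol set, because they do not define one or identify crossovers. This is an inexpensive improvement to make before outcomes are seen.

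**What to change.** In section 12.2:

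1. Keep intent-to-treat as primary. Pre-specify a per-protocol analysis of 24-month response in randomized, eligible participants who received the assigned treatment, with the same Farrington-Manning test and interval.
2. Report initial crossovers by arm, and say that a non-inferiority claim will be interpreted with caution if the two sets disagree.
3. State how initial crossovers are scored in the primary analysis.
4. Carry the treatment-failure rule of section 4.3 into section 12 for the 24-month endpoint.
5. Reconcile the drop-and-replace and withdrawal rules (4.3, 7.4) with the all-randomized set (12.2, 12.3).
6. State the sidedness of the non-inferiority test.

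The cost is wording and one further run of the same test. The per-protocol set is smaller and has less power (about 79, 77 or 74% with 5, 10 or 15% excluded). It loses the protection of randomization and is biased if crossover is related to prognosis. For that reason a hard rule that both sets must succeed is a trade-off for the sponsor to weigh and is not part of this fix.

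### Does the missing side of the 0.05 level make the stated 80% power, or the hoped-for cushion, wrong?

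*Combined protocol and SAP*

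**What the plan says.** Section 12.2 sets one-directional hypotheses: the null is that the PDT response probability lies at or below the surgery probability minus the margin. On the method it says "we will be using the approach of Farrington-Manning to test our hypothesis via a score based test". The margin is 20 percentage points, and the "Farrington-Manning based test will be performed in conjunction with a 0.05 nominal significance level". No side is given there. With 57 per arm, "there is approximately 80% power associated with the non-inferiority test when the true tumor response probabilities are equal to 85% in both groups", and "The calculation was carried forth using SAS PROC POWER"; the procedure's options are not listed. The synopsis repeats the power without a level.

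The next paragraph of 12.2 describes the quality-of-life mixed model. Near its end it says "All tests will be two-sided and tested at a 0.05 nominal significance level". This is the only statement of side in the section.

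Section 12.1 assumes 85% complete response in both arms and adds: "We also wish to provide a bit of a cushion in case the surgical response rate is much higher than 85" (per cent). It attaches no rate or power to that wish.

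The endpoint is "non-inferiority of PDT compared to standard of care with regards to tumor response at 24 months post-procedure". On missing data, 12.2 says "No method of imputation will be used for missing data". The synopsis and 12.3 count every randomized participant as evaluable for response.

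**The concern.** A one-directional hypothesis beside a bare 0.05 is easily read as one-sided 0.05. On that reading the planned test has about 89% power, not 80%, so level and power seem to disagree. The side also fixes the critical value, 1.645 or 1.960, and some data sets pass one and fail the other. In an open-label trial nobody wants that value chosen after the results are known.

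The cushion sentence adds to the unease. A reader might take it to mean that the design tolerates a surgery arm well above 85%, which the power figures do not support if PDT stays at 85%.

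**Working it through.** **Inputs.** From 12.2: n = 57 per arm, margin 0.20, true rates 0.85 and 0.85, Farrington-Manning score test, level 0.05 with no side given.

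**Step 1: the stated power, for the planned test.** The null variance uses the maximum-likelihood rates restricted to a difference of 0.20. At true rates 0.85/0.85 these are 0.7077 (PDT) and 0.9077 (surgery).

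- Null standard error: s0 = √[(0.7077×0.2923 + 0.9077×0.0923)/57] = 0.07141.
- Alternative standard error: s1 = √[(2×0.85×0.15)/57] = 0.06689.
- Power = Φ[(0.20 − z×s0)/s1].

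| One-sided level | z | (0.20 − z×s0)/s1 | Asymptotic power | Exact power |
|---|---|---|---|---|
| 0.025 | 1.960 | 0.898 | 81.5% | 83.2% |
| 0.05 | 1.645 | 1.234 | 89.1% | 89.8% |

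Exact power sums the binomial probabilities of every rejecting outcome among the 58×58 possible ones. The stated figure of about 80% agrees with one-sided 0.025, that is, two-sided 0.05. It does not agree with one-sided 0.05. For 80% power the asymptotic formula needs 55 per arm at one-sided 0.025 and 44 at one-sided 0.05.

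**Step 2: another route to 57.** An ordinary pooled-variance comparison of 85% with 65% has mean rate 0.75.

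- s0 = √[(2×0.75×0.25)/57] = 0.08111.
- s1 = √[(0.85×0.15 + 0.65×0.35)/57] = 0.07892.
- At one-sided 0.05: Φ[(0.20 − 1.645×0.08111)/0.07892] = Φ(0.844) = 80.06%.
- At one-sided 0.025: Φ(0.520) = 69.8%.

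This is not the test named in 12.2, but it shows that the power figure alone cannot reveal which options were used.

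**Step 3: what the side is worth.** With 49/57 responders on surgery:

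- PDT 45/57: difference plus margin = 0.1298, standard error 0.0727, z = 1.785. This passes at 1.645 and fails at 1.960.
- PDT 46/57: 0.1474/0.0721 gives z = 2.044. This passes both.

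At 85/85 the two levels give opposite verdicts in 89.80% − 83.22% = 6.6% of trials. Exact type I error at PDT 65% and surgery 85% is 2.6% at one-sided 0.025 and 5.2% at one-sided 0.05.

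**Step 4: the cushion.** Exact power of the planned test:

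| PDT | Surgery | One-sided 0.025 | One-sided 0.05 |
|---|---|---|---|
| 85% | 85% | 83% | 90% |
| 85% | 88% | 73% | 82% |
| 85% | 90% | 64% | 75% |
| 85% | 95% | 37% | 50% |
| 90% | 90% | 92% | 96% |

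With PDT fixed at 85%, exact power stays at or above 80% while surgery is no higher than 86.0% (one-sided 0.025) or 88.6% (one-sided 0.05). The tolerance is small but not zero. If both rates rise together, power rises.

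**The case for a change.** The strongest case for a change is that the two-sided sentence may not reach the primary test at all. It follows mixed-model contrasts and informative missingness and comes just before diagnostic plots, all of them quality-of-life matters. The hypotheses point one way, PROC POWER is cited without options, and the pooled calculation reaches 57 per arm at one-sided 0.05. So the documents do not prove which level was meant, and the choice can turn a verdict.

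Much of this is true. The placement is awkward and the software options are unrecorded. But 12.2 is not silent on side: it makes one general statement, worded to cover all tests. Applied to the primary test, that statement gives the level at which the named method has the stated power. The competing route needs both a different test from the one in 12.2 and a narrower reading of that sentence. A statistician applying the text would use 1.960, the more stringent value.

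On the cushion, it is fair to say that no figure supports the sentence and that protection is weak when surgery reaches 90% to 95% and PDT stays at 85%. But the text speaks of a wish. It does not say whether the cushion comes from the sample size or the margin, and it does not hold PDT at 85%. Treating it as a promise of 80% power goes beyond what is written.

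One could also ask for power at a lower PDT rate. At the 82% quoted in 12.1, with surgery at 85%, exact power is 67% at one-sided 0.025 and 77% at one-sided 0.05. That is useful context, but leaving it out of a phase II sample-size section is not an error.

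**Conclusion.** The concern does not call for a change. The side of the primary level is a gap in wording that analysts fill sensibly: the general two-sided 0.05 statement implies one-sided 0.025, and there the planned test has 81.5% power (83.2% exact) against a stated figure of about 80%. A one-line clarification would be tidy, but it would leave the 57 per arm, the 20-point margin and the Farrington-Manning test as they are.

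The cushion sentence is loose commentary. Removing it or adding a power table would alter neither what the trial does nor what it can conclude.

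This rests on two assumptions. The first is that the two-sided statement covers the primary test; if one-sided 0.05 was meant, power is about 89% to 90% and the stated figure errs on the cautious side. The second is that all 57 per arm are evaluable, as the synopsis and 12.3 state. Whether that is realistic at 24 months without imputation is a separate question.
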